The period of IMI risk is defined as the period of active anticancer treatment. Exposure data from cohort subjects are collected from the date of cancer diagnosis until finished first-line chemotherapy, IMI occurrence, death, emigration, switching to a non-first-line treatment (e.g., treatment for induction failure or relapse), or 31st December 2022 (end of the study period), whichever comes first. For the IMI patients, we will also collect IMI outcome (cured, deceased, or emigrated) data after the IMI diagnosis for a narrative description of this group and to calculate the fatality rate.

Figure 1. STROBE flow diagram presenting the study design. ITS, intention to survey; ALL, acute lymphoblastic leukemia; AML, acute myelogenous leukemia (AML); IMI, invasive aspergillus.

Bias and limitations

As the cohort study is observational and retrospective, the study relies on data extracted from medical charts. To avoid imprecise documentation, the predominant amount of data is exact (i.e., blood values), whereas more loosely medical chart statements will be avoided as far as possible. There is no risk of 'recall bias,' as no patients or health care professionals will be contacted.

Another limitation in our study could be a small number of IMI patients and exposures; this would yield a low power and could be the reason for inconclusive findings. To avoid this and type 1 errors, we will report measures of association with confidence intervals; if these exclude measures of clinical interest, we will assume that our study is not limited by sample size and number of events (say, if the 95% confidence intervals around the Hazard Ratio reasonably precise [95%CI: 0.80 to 1.25]).

During the 15 years of study, the treatment protocols have changed. We will apply the analyses to the whole population and do subgroup analyses for patients according to their specific treatment protocols.

Statistical methods

The primary analyses will be based on the Intention to Survey (ITS) population, i.e., based on the Full Analysis Set (see Figure 1 illustrated above). To assess distributions and check for errors, variables will be summarized before analysis. The frequency of IMI in the cohort will be determined by calculating the cumulative incidence.

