Hazard ratios (HR) for ALL relative to AML will be estimated, with two-sided 95% confidence intervals, based on a Cox proportional-hazards model, with AL-type as the primary covariate. Equivalence will be shown if the limits of the two-sided 95% confidence interval exclude (less than) 0.80 and (more than) 1.25. Crude incidence rates will be expressed in patients with IMI events per 100 patient-years, with two-sided 95% confidence intervals. No multiplicity adjustments will be applied. P values, without adjustment for multiplicity, will be produced for all listed objectives. To identify independent risk factors for the development of IMI, regression models will be applied to explore which children were more likely to develop IMI (e.g., AL-type, sex, age at diagnosis, and related toxicities, see table 2).

All *P* values and 95% confidence intervals will be two sided. We will not apply explicit adjustments for multiplicity, rather we will analyze the secondary objectives in a prioritized order: The analyses of these will be performed in sequence until one of the analyses fails to show the statistically significant difference, or until all analyses have been completed at a statistical significance level of 0.05. The key secondary statistical tests will be reported with *P* values for hypothesis tests and claims of statistical significance.

Analyses will be performed using STATA software version 17 (StataCorp. 2021. Stata Statistical Software: Release 17. College Station, TX: StataCorp LLC.).

Patient and public involvement statement

As all data will be retrieved from patients no longer in active treatment, patients are not actively involved and were unfortunately not included in designing this study.

Ethics and dissemination

The relevant Danish authorities have approved the study, including the regional research legislation office "Regionssekretariat og jura, Syddanmark" (journal no. 22/7692), "Region Syddanmarks Interne Fortegnelse" (journal no. 22/15850), and by the involved departments. Other ethics approval has not been required for this study.

The study will be registered at Clinical.Trials.gov. The study acts under the Declaration of Helsinki. No patient will be contacted and is not exposed to any inconvenience. All data are confidential and will

be processed in accordance with the General Data Protection Regulation (GDPR) and The Danish Data Protection Act.

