Abbreviations: BAL, bronchoalveolar lavage; CSF, cerebrospinal fluid; CT, computed tomography; PCR, polymerase chain reaction; IMI, invasive mold infection.

alf culture is available, append the identification at the genus or species level from the culture results.

^b Tissue and cells submitted for histopathologic or cytopathologic studies should be stained using Grocott-Gomori methenamine silver stain or periodic acid Schiff stain to facilitate inspection of fungal structures. Whenever possible, wet mounts of specimens from foci related to invasive fungal disease should be stained with a fluorescent dye (eg, calcofluor or blankophor).

Recovery of Aspergillus species from blood cultures rarely indicates endovascular disease and almost always represents contamination.

^dHematologic malignancy refers to active malignancy, in receipt of treatment for this malignancy, and those in remission in the recent past. These patients would comprise largely acute leukemias and lymphomas, as well as multiple myeloma, whereas patients with aplastic anemia represent a more heterogeneous group of individuals and are not included. The list of host factors has been shortened.

Table 2. Characteristics and putative risk factors to be collected from all cohort patients.

	VARIABLE
Age (number in years)	Numerical
Sex (male/female)	Binary
Treating facility (Copenhagen/Århus/Odense/Aalborg)	Categorical
Pre-leukemia comorbidities	Categorical
ALL diagnosis: treatment protocol, risk group and CNS-status	Categorical
AML diagnosis: treatment protocol, risk group, FAB, and CNS-status	Categorical
Date of malignancy diagnosis	-
Name of treatment protocol	Categorical
Criteria met for IMI (proven/probable)	Categorical
Localization of IMI	Categorical
Neutrophil granulocyte count at leukemia diagnosis	Numerical
Anemia and red blood cell transfusion requirement (quantity)	Numerical
Thrombocytopenia and platelet transfusion requirement (quantity)	Numerical
Primary antifungal prophylaxis (type/dose/duration)	Categorical
Fungal infection other than IMI (fungi in a sterile site) (localization and type)	Categorical
Concomitant infections (bacteria in a sterile site) (localization and type)	Categorical
Neutropenic colitis (only radiological evidence: MRI, CT, plain film of the abdomen, US: bowel wall thickening > 4 mm, mesenteric stranding,	Binary
bowel dilatation, mucosal enhancement, or pneumatosis) (yes/no)	
Pancreatitis (> x3 upper limit of amylase/lipase) (yes/no)	Binary

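### Minor: protocol subgroups cannot adjust the ALL-versus-AML hazard ratio for treatment era, and the interval method for toxicities with no exposed mold-infection case is not fixed

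*Combined protocol and SAP*

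**What the plan says.** The section Bias and limitations of the combined protocol and SAP names two difficulties and a response to each.

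- Treatment change: "During the 15 years of study, the treatment protocols have changed". The response is "We will apply the analyses to the whole population and do subgroup analyses for patients according to their specific treatment protocols".
- Sparse data: "Another limitation in our study could be a small number of IMI patients and exposures". The response is that "we will report measures of association with confidence intervals". If the intervals exclude values of clinical interest, the study will be taken as not limited by its size.

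Under Statistical methods, the main comparison is an HR for ALL relative to AML, "based on a Cox proportional-hazards model, with AL-type as the primary covariate", with equivalence limits of 0.80 and 1.25. For objective 3 the plan says: "To identify independent risk factors for the development of IMI, regression models will be applied to explore which children were more likely to develop IMI", with a pointer to Table 2. It names no interval method and no method for sparse data.

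Table 2 lists protocol inside each diagnosis ("ALL diagnosis: treatment protocol, risk group and CNS-status", with a parallel AML row) and again as a general item. It also lists the date of diagnosis, and neutropenic colitis, pancreatitis and insulin-dependent diabetes as yes/no variables.

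**The concern.** Each response leaves part of its own problem open.

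**Era.** A subgroup containing only ALL or only AML patients holds no contrast between the two, and protocol indicators entered beside leukemia type would be aliased with it. If the AML share of new patients drifted while mold-infection risk changed, the whole-population HR would mix leukemia type with era. The plan states no analysis of that HR that separates them.

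**Empty cells.** When no infected child had a given toxicity, the ordinary partial likelihood has no finite maximum. The HR runs to zero and the Wald interval runs from zero to infinity. This happens in a one-variable model too, so it is not a matter of model size. Reporting an interval is then no remedy for that factor unless a method that copes with an empty cell has been chosen, and the choice affects what is concluded.

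**Working it through.** **Inputs.** Cohort of about 800 (Study population). Cited rates of invasive aspergillosis: AML 14/232, ALL 33/1216 (introduction). The AML share is assumed equal to that in the cited series, 232/1448 = 16%. Toxicity prevalences, drift in AML share and treatment durations are not in the documents and are assumed.

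**1. The plan's own figures.** 14/232 = 6.03% and 33/1216 = 2.71%, as stated.

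**2. Expected events.** AML: 800 × 0.160 × 0.0603 = 7.7. ALL: 800 × 0.840 × 0.0271 = 18.2. The total is 26.0 (Poisson 95% range 16-36). An AML share of 10% or 25% gives 24.4 or 28.4. Because the cited rates cover aspergillosis only, all molds together could give more.

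**3. Precision of the main HR.** SE(log HR) = √(1/7.73 + 1/18.23) = 0.429, and exp(1.96 × 0.429) = 2.32. The ratio of upper to lower limit is 2.32² = 5.4, against 1.25/0.80 = 1.56 between the equivalence limits. With 36 events split in the same proportion, the ratio is still 4.2.

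**4. Size of an era bias.** Take three equal eras and a leukemia effect constant over eras. The unstratified-to-stratified ratio is the share-weighted mean hazard in ALL divided by that in AML.

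| AML share by era | Relative hazard by era | ALL mean | AML mean | Ratio |
|---|---|---|---|---|
| 16/16/16% | 1/0.7/0.5 | 0.733 | 0.733 | 1.00 |
| 12/16/20% | 1/0.7/0.5 | 0.741 | 0.692 | 1.07 |
| 20/16/12% | 1/0.7/0.5 | 0.725 | 0.775 | 0.94 |
| 10/16/25% | 1/0.6/0.33 | 0.663 | 0.546 | 1.21 |

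Example, row 2: ALL (0.88 + 0.84 × 0.7 + 0.80 × 0.5)/2.52 = 0.741; AML (0.12 + 0.16 × 0.7 + 0.20 × 0.5)/0.48 = 0.692. Large simulated cohorts with staggered entry gave the same ratios.

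**5. Does it alter the equivalence verdict?** By step 3, the interval cannot fit inside 0.80-1.25 wherever it is centered. The HR may also lie far from 1. With assumed treatment times of 2.5 years for ALL and 0.5 or 1 year for AML, the cited rates give (2.71/2.5)/(6.03/0.5) = 0.09, or 0.18. Raised by 21% and multiplied by 2.32, these reach about 0.25 and 0.50, still below 0.80.

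**6. Chance of no exposed case.** This is (1 − q)^D, with D events and q = p·HR/(p·HR + 1 − p).

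| Prevalence p | True HR | q | D = 26 | D = 36 to 16 |
|---|---|---|---|---|
| 5% | 1 | 0.050 | 26% | 16-44% |
| 10% | 1 | 0.100 | 6% | 2-19% |
| 5% | 2 | 0.095 | 7% | 3-20% |
| 10% | 2 | 0.182 | 0.5% | 0.1-4% |

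**7. What an ordinary fit returns.** In a simulated cohort of 800 with 28 events, 18 exposed children and no exposed event, the Cox fit did not converge: HR about 5 × 10⁻¹², SE of the log HR about 5 × 10⁵, Wald interval 0 to infinity.

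**8. Upper limit by method, 26 events, none exposed, 5% prevalence.**

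- Unpenalised profile likelihood: 0.95 × (exp(3.84/52) − 1)/0.05 = 1.46.
- Firth penalised, profile limits (median of 40 simulated cohorts): HR 0.35, 95% CI 0.003-2.5.
- Exact: q_U = 1 − 0.025^(1/26) = 0.132, so HR_U = 0.132 × 0.95/(0.868 × 0.05) = 2.9.

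A doubled risk is excluded by the first method and not by the other two.

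**The case against.** On era, the plan never says that protocol subgroups adjust the main HR, and objective 1 is to determine and compare incidence. Protocol is a listed exposure, and the Table 2 regressions could take in diagnosis date. If protocols succeeded one another, protocol-specific results would also show risk changing within each leukemia. All this stands, but nothing commits the plan to a calendar term in the ALL-versus-AML model. That protocols are leukemia-specific is an inference from the table's layout; a shared protocol would allow a within-protocol contrast.

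A reader might infer that the main HR is confounded by era, or that a 21% shift matters because it nearly spans the distance from 1 to 1.25. The documents give no sign of drift in the AML share, and step 5 shows that no equivalence verdict turns on it.

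On sparse data, the plan does not say that its intervals are Wald intervals, and profile and exact methods give finite limits. So it would be wrong to say that confidence intervals fail in general. Nor would an interval from zero to infinity pass as strong protection under the plan's own rule, since it excludes nothing of clinical interest. The stopping rule, "The analyses of these will be performed in sequence until one of the analyses fails to show the statistically significant difference", further restrains claims. What stands is that neither rule supplies a usable estimate, and that the method is left open where it matters. The example also depends on prevalence: at 10%, the penalised interval for an empty cell is 0.0013-1.18, which does exclude a doubling.

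**Conclusion.** The point holds as a minor one.

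- The planned protocol subgroups cannot adjust the ALL-versus-AML HR for treatment era if protocols are leukemia-specific, and no other handling of calendar time is stated. The bias is about nil with a stable AML share, 6-7% under moderate assumed drift and about 21% in an extreme scenario. It is small beside a factor of 2.3 each way.
- With about 26 expected events, an empty cell for a toxicity of 5% prevalence is quite likely if there is no effect (26%) and possible even if risk is doubled (7%). In that case an ordinary Cox fit with Wald limits is unusable, and the alternatives disagree (1.5, 2.5 or 2.9), so the method should be fixed before the data are seen.

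The empty-cell chances rest on the cited aspergillosis rates, a 16% AML share and assumed prevalences, and treat each exposure as constant over time.

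**What to change.** Add to Statistical methods:

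> Beside the whole-population estimate, the ALL-versus-AML HR will be reported as a sensitivity analysis with the baseline hazard stratified by calendar period of diagnosis (2008-12, 2013-17, 2018-22). Protocol-specific results are descriptive within leukemia type. All binary Table 2 toxicity factors will be fitted with Firth-type penalised likelihood and profile-likelihood 95% CIs, whatever the number of exposed cases, and that number will be shown.

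One method throughout is preferable to a switch at a low count. A trigger of fewer than five exposed cases would fire with probability 99%, 89% or 38% at prevalences of 5%, 10% or 20% (26 events, no effect), and the choice of method would then depend on the data. In 1,600 simulated penalised fits at 5% and 10% prevalence and HR 1 or 2, every estimate was finite and profile coverage was 95.0-97.5%.

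**Cost.** No new data are needed, and the whole-population HR stays as planned. The penalised fit shrinks estimates slightly. Whether the named software fits a penalised Cox model with profile limits must be checked; a second package may be needed. In simulation, era strata raised the SE of the log HR by a median of 0.1% with a stable AML share and 0.7% with a 12-to-20% drift.

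**Limits.** Era strata remove only changes common to both leukemias. When only the AML hazard was halved in simulation, within-era HRs moved from 0.068 to 0.138 while the stratified and unstratified HRs both stayed at 0.09. With 7.7/3 = 2.6 AML events per era, such a change can only be described. The wording also does not settle the timing of toxicities relative to infection.

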Few studies have examined the incidence according to the currently used "European Organization for Research and Treatment of Cancer/Invasive Fungal Infections Cooperative Group and the National Institute of Allergy and Infectious Diseases Mycoses Study Group" (EORTC/MSG) guidelines for a proven, probable, or possible IMI (3). An Australian 10-year epidemiological study, however, indicates an incidence of invasive aspergillosis in patients treated for acute myelogenous leukemia (AML) and acute lymphoblastic leukemia (ALL) of (14/232) 6%, (33/1216) 2.7 %, respectively (4, 5). Only few epidemiologic reports have been performed in Denmark or Scandinavia (6).

Despite progress in the diagnosis, prevention, and management of IMI, the reported mortality rates are often high. In an epidemiologic multicenter study, the main proportion of molds was A. fumigatus, with a mortality rate of 30% (7). A number of risk factors have been associated with IMI, among these, corticosteroid exposure, neutropenia, as well as different chemotherapy and conditioning regimens. However, few studies have addressed this in children with cancer, and knowledge regarding individual risk prediction for developing IMI in immunosuppressed children remains sparse (8, 9). Besides established risk factors for IMI, other treatment-related toxicities, including metabolic changes and gastrointestinal toxicity, may also be related to infectious morbidity (10-12).

Our aim is to obtain an epidemiological overview of IMI in children receiving first-line treatment for ALL or AML in Denmark and identify possible risk factors, including treatment-related adverse effects.

Objectives

1. To determine and compare the incidence of IMI in childhood AML and ALL during first-line chemotherapy in Denmark.

2. To determine and compare the mortality of IMI in childhood AML and ALL during first-line chemotherapy in Denmark.

3. To explore risk factors for IMI in childhood AML and ALL during first-line chemotherapy in Denmark.

METHODS

Study design

A retrospective nationwide multicenter, open cohort study of all children who received first-line chemotherapy against acute leukemia from January 1st, 2008, to December 31st, 2022, in a Danish pediatric oncology unit; this includes data from the four Danish tertiary pediatric oncology units at Rigshospitalet, Aarhus University Hospital, Odense University Hospital, and Aalborg University Hospital.

Study population

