Any patient (<18 years) who initiated first-line chemotherapy against primary ALL or AML at any of the four Danish departments of pediatric oncology from January 1st, 2008, to December 31st, 2022 (**Figure 1**). The eligible sample of children has been estimated to correspond to approximately 800 individuals who will be included in the cohort and subsequently be referred to as the intention-to-survey (ITS) population.

Data sources

Patients from the four Danish departments of pediatric oncology treating pediatric ALL and AML will be identified by searching the Danish Childhood Cancer Registry. The register holds data since 1985 on all children < 15 years with cancer and all children 15-17 years of age treated at a pediatric oncology department (13).

After cohort inclusion, data will be collected from the databases below, including the patient's medical records, hospital administrative databases, and national databases when applicable. The data for all cohort patients will be collected as listed in **Table 2**. For IMI patients only, additional data for a qualitative synthesis is collected, as detailed in **Table 3**.

- **The Danish Microbiology Database** is a nationwide database carrying all microbiology test results. We will search the database to identify factors that fulfill the criteria of direct or indirect proof of mold infection (Table 1).
- **The Danish Pathology Register is** a nationwide database carrying all pathology test results. We will search the database to identify histopathologic proof of mold infection.
- We will search the regional radiology databases for proof of mold infection, as this is not a nationwide database. We will explore the databases for radiologic interpretations of computed tomographies and magnetic resonance imaging to identify the IMI criteria (Table 1).
- Regional databases of blood test results will be searched to identify the neutrophilic count at the time of mold diagnosis in the IMI group and further to find proof of pancreatitis or hyperlipidemia.
- Patient records will be scrutinized to identify pre-leukemia comorbidities, leukemia diagnosis, and risk group, among other information, as listed in table 2 and table 3.

Data collection will start in April 2023.

Outcome variables

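### Protocol subgroup analyses are planned without a test of whether risk-factor effects differ between protocols and without a descriptive label, so a shared risk factor can often look protocol-specific

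*Combined protocol and SAP*

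**What the plan says.** Under Bias and limitations, the plan notes that treatment protocols changed over the 15 years and answers this with: "We will apply the analyses to the whole population and do subgroup analyses for patients according to their specific treatment protocols". The number of protocols, a minimum number of events per protocol and the way protocol-specific results will be compared are not given.

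Under Statistical methods, the risk-factor analysis is described as follows: "To identify independent risk factors for the development of IMI, regression models will be applied to explore which children were more likely to develop IMI". The same section says "No multiplicity adjustments will be applied" and "P values, without adjustment for multiplicity, will be produced for all listed objectives". Tests are two-sided at 0.05. The prioritized testing order in that section covers the secondary objectives and does not mention the protocol subgroups.

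No section names a factor-by-protocol interaction or any other heterogeneity test. Objective 3 and the risk-factor models are worded as exploration. The protocol subgroups carry no such label.

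**The concern.** Once results are split by protocol, the natural reading is to see in which protocols a factor reaches significance. With few events per protocol, that pattern depends largely on chance and on how the events happen to be divided. A factor that acts equally in every protocol can reach P < 0.05 in one and miss it in another, and it may then be reported as belonging to that treatment protocol. Each extra subgroup is also another chance for a factor with no effect to appear as a risk factor under one protocol. The plan contains no analysis that would tell a real difference from this.

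At stake is the interpretation of Objective 3. The main whole-population estimates are not affected.

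**Working it through.** **Plan's own figure.** The documents give no event count, power or sample-size calculation, so there is nothing to reproduce beyond the two cited rates: 14/232 = 6.0% (AML) and 33/1216 = 2.7% (ALL).

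**Inputs from the documents.**
- Cohort size, from Study population: "The eligible sample of children has been estimated to correspond to approximately 800 individuals".
- Background rates, from the text before Objectives. They refer to invasive aspergillosis and serve here as a proxy for IMI.
- Two-sided 0.05, from Statistical methods.

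**Assumed, because the documents do not say.** 100–160 children with AML, 2–6 protocols, 10–50% of children exposed to the factor, and a common true HR of 1 to 4.

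**Step 1: expected events.** E = 0.06 × n_AML + 0.0271 × (800 − n_AML).
- n_AML = 100: 6.0 + 19.0 = 25.0
- n_AML = 120: 7.2 + 18.4 = 25.6
- n_AML = 160: 9.6 + 17.3 = 26.9

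So about 26. The outer bounds are 22 (all children at the ALL rate) and 48 (all at the AML rate).

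**Step 2: formula check with equal protocols, 50% exposed.** Power in one protocol with d events is Φ(√(d × 0.5 × 0.5) × ln HR − 1.96). With k protocols, each with power π, the chance that some but not all are significant is 1 − π^k − (1 − π)^k.
- HR 2, k = 4: d = 26/4 = 6.5. Power is Φ(1.275 × 0.693 − 1.96) = Φ(−1.08) = 0.14. Mixed: 1 − 0.14⁴ − 0.86⁴ = about 0.46.
- HR 3, k = 4: power is Φ(1.275 × 1.099 − 1.96) = Φ(−0.56) = 0.29. Mixed: about 0.74.
- Over k = 2 to 6, the mixed share is 20–32% at HR 1.5, 36–50% at HR 2, 50–75% at HR 3 and 42–88% at HR 4.
- At HR 2, no protocol at all is significant in about 50–58%.

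**Step 3: simulation with small counts.** The normal approximation is rough at so few events, so the counts were simulated directly. Event counts per protocol are Poisson, for example with means 13/13, 9/9/4/4 or 6/6/6/3/3/2. With exposure prevalence p, each event is in an exposed child with probability p·HR/(p·HR + 1 − p). Each protocol is tested with a score test, z = (x − np)/√(np(1 − p)), where x of its n events are in exposed children, and with an exact binomial test.

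| Result | Score test | Exact test |
|---|---|---|
| HR 1: significant in at least one protocol | 8–23% | 4–9% |
| HR 1.5–2 in all: significant in some, not all | 20–63% | 8–39% |
| HR 2.5 in all: significant in some, not all | 43–76% | 21–54% |

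The choice of test matters. At 10% exposed, a protocol whose single event is in an exposed child gives z = 0.9/0.3 = 3.0 by the score test, although the exact P is 0.10. A Wald test with 4–6 protocols and 10–30% exposed gives 28–47% mixed at HR 2 and 40–60% at HR 2.5.

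**Step 4: comparison.** When the effect is truly common, one heterogeneity test across protocols signals a difference in about 3–6% of simulated studies, close to the nominal 5%.

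**The case against.** Several points on the other side stand. The plan keeps the whole-population analysis, words Objective 3 and its models as exploration, admits that events may be few, and promises confidence intervals for measures of association. Unadjusted P values are promised for the listed objectives, and the protocol subgroups are not a listed objective, so subgroup P values are not expressly promised. Treatment protocol is itself an exposure in Table 2, so protocols can be compared as a main effect.

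These points soften the concern but do not remove it. A main effect of protocol does not show whether another factor's effect differs between protocols. Separate intervals do not test a difference, and they will be very wide. At HR 1 with 50% exposed, 26 events give limits of exp(±1.96/√6.5), or 0.46 to 2.16. With 6.5 events they are exp(±1.96/√1.625), or 0.21 to 4.65.

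A reader might also infer more than the documents support:
- **That every analysis is repeated in each protocol.** The sentence does not say so. Table 2 records protocol separately for ALL and AML. If protocols are specific to leukemia type, the ALL–AML hazard ratio cannot be estimated within one.
- **That a shared factor will usually look protocol-specific.** This depends on the assumed HR, number of protocols and test. At HR 2 or below it is often less likely than not.
- **That significance counts are the only possible reading, or that the subgroups exist to show whether risk factors hold across protocols.** The plan states neither. No section says that a factor will be claimed as protocol-specific.

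**Conclusion.** The concern holds in this form: the plan splits the analyses by treatment protocol but has no test of whether a risk factor's effect differs between protocols, and it does not label the subgroup results descriptive. A shared factor can then often look protocol-specific, several times more often than under one heterogeneity test in most settings examined. The factor ranges from about 8/5 = 1.6 at the low end (exact test, weak effect) to 76/5 = 15 at the high end (score test, HR 2.5, six protocols). Inflation for a factor with no effect is clear with the score test and small or absent with exact tests.

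The size rests on about 26 events from proxy rates and on assumed numbers of protocols, exposure prevalence and effect size, none of which the documents give. The absence of a planned comparison does not depend on those assumptions. This is an inexpensive improvement to a secondary part of the plan, not a fault in the main analysis.

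**What to change.** Replace the sentence on subgroup analyses under Bias and limitations with:

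> The whole-population analysis is the main analysis. For risk factors other than AL-type and treatment protocol, the whole-cohort Cox model is stratified by treatment protocol; AL-type and treatment protocol are estimated in models not stratified by protocol. For a short prespecified list of factors, whether the association differs between protocols is judged by one factor-by-protocol interaction test per factor, with protocols of the same leukemia type grouped where events are few. Protocol-specific hazard ratios are shown with 95% confidence intervals, without P values, as descriptive, and no claim that a risk factor is confined to one protocol is made from them.

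The exception for AL-type and treatment protocol is needed because a stratification variable has no hazard ratio. Stratifying every model would make the effect of protocol inestimable and, if protocols are leukemia-specific, that of AL-type as well.

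**Cost.** A wording change, a stratified model and one interaction test per listed factor, all using protocol data already in Table 2. The interaction test has low power at about 26 events, so finding no evidence of a difference must not be read as proof of a common effect. Protocols without events add nothing to the stratified estimate.
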